#### Protocol:

Subjects will be required to fill up the consent form and history taking will be carried out on all subjects. Subjects will be tested using the Ocular Surface Disease Questionnaire (OSDI) (Ngo et al., 2017) before recruitment in order to classify subjects if they have dry eye symptoms (inclusion criteria). Visual acuity testing using log MAR Acuity Chart (Johnston, 2016) as well as anterior segment assessment using slit lamp biomicroscopy will be done prior to the study in order to know the baseline Visual acuity and ocular condition of the subjects' eyes.

#### **Phase 1**

First measurement of TBUT (Mcmonnies, 2018) on both eyes will be taken before lens insertion. Then, subjects will be fitted with therapeutic VCO contact lens on one of their eyes and a placebo hydrogel contact lens on the other eye which acts as a control. The contact lenses will be fitted in randomized manner by a mask operator. Subjects will wear the contact lenses for 15 minutes. After the 15th minute, both contact lenses will be removed and second measurements of TBUT will be done. All tear breakup time (TBUT) measurements will be taken three times and the average value will be used as the data. These will be the immediate measurement after therapeutic VCO contact lens wear. Subjects will be given 15 minutes time interval before a re-measurement of TBUT test again. Once all the measurements are taken, subjects will be discharged from the study before being called again in Phase 2. From the data collected, an analysis will assist to understand the mechanism of tear integrity when VCO therapeutic contact lens is used on dry eyes.

#### **Phase 2**

First measurement using Schimer's Test (Miyake et al, 2016) on both eyes will be taken before lens insertion. Then, subjects will be fitted with therapeutic VCO contact lens on one of their eyes and a placebo hydrogel contact lens on the other eye which acts as a control. The contact lenses will be fitted in randomized manner by a mask operator. Subjects will wear the contact lenses for 15 minutes. After the 15th minute, both contact lenses will be removed and second measurements of Schimer's Test will be done. All measurements will be taken three times and the average value will be used as the data. These will be the immediate measurement after therapeutic VCO contact lens wear. Subjects will be given 15 minutes time interval before a re-measurement of Schimer's Test again. Once all the measurements are taken, subjects will be discharged from the study before being called again in Phase 3. From the data collected, an analysis will assist to understand the mechanism of tear volume changes when VCO therapeutic contact lens is used on dry eyes.

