## Problem statement

It is known that VCO drops used as ocular rewetting agent on rabbit eyes has been tested and proven safe and effective in increasing tear volume. It has also been tested on humans with success. However, the use of contact lens as a vehicle to transfer the VCO need to be further investigated. It is significantly important to know the role of VCO therapeutic contact lens in changing the tear volume and stability in dry eye patients. Hence, this study will determine if VCO Therapeutic Contact Lens changes the tear volume and stability in dry eye patients.

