## Objective

The main aim of research is to investigate the changes of tear volume and tear stability from VCO Therapeutic Contact Lens wear.

The following specific objectives are: -

- (i) To determine the tear break up time (TBUT) and tear volume (Schirmer's Test) at 0 and 15 minutes after therapeutic VCO contact lens wear.
- (ii) To determine the tear break up time (TBUT) and tear volume (Schirmer's Test) at 15 minutes after lens removal.
- (iii) To measure the inter-variability and intra-variability of the parameters measured for TBUT, after therapeutic VCO contact lens wear

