Virgin coconut oil (VCO) is known as a local functional food and contain antiviral and anti-microbial agents (Marina & Man 2016). Study has been conducted on efficacy of VCO as ocular rewetting agent on rabbit eyes. It has been shown that VCO did not cause harmful effects when used on rabbit's eyes. The fatty acid and anti-inflammatory agents on VCO may act as protective layer over the tear film layers to reduce evaporation, which is useful for those with dry eyes problem (Mutalib et al. 2015). Similar study was done on human and it was found to increase the tear volume (Macmonnies, 2018)

However, one of the discomforts when using the VCO, it is oily and messy when used directly on eyes and it also causes temporary blurriness. In another successful study, contact lenses were used as a medium or vehicle of transportation of VCO to human eyes (Hussin, 2014). The contact lenses were immersed in a volume of VCO for several hours before placing it on the human eyes. In this study, VCO extracts will be injected out and will be vehicle to the eye by using hydrogel contact lens. This study will investigate the role of VCO Therapeutic Contact Lens in changing the tear volume and tear stability in dry eye subjects.

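### The Schirmer reading taken straight after lens removal cannot tell a rise in tear volume from residual VCO or a VCO-specific reflex response, and the plan names neither a deciding time point nor a VCO-versus-placebo comparison

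*Combined protocol and SAP*

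**What the plan says.** The Hypothesis claims improvement in both tear volume and tear stability. The Objective section ties volume to a single instrument: "tear volume (Schirmer's Test) at 0 and 15 minutes after therapeutic VCO contact lens wear". Objective (ii) adds a reading 15 minutes after the lens is taken out.

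Phase 2 is the only phase that uses the Schirmer test; Phases 3 and 4 repeat tear break-up time. It takes a pre-insertion reading in both eyes and then fits a VCO lens in one eye and "a placebo hydrogel contact lens on the other eye which acts as a control". It continues: "After the 15th minute, both contact lenses will be removed and second measurements of Schimer's Test will be done". A third reading follows: "Subjects will be given 15 minutes time interval before a re-measurement of Schimer's Test again". On replication: "All measurements will be taken three times and the average value will be used as the data".

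The lens is a delivery device. The Problem statement says that "the use of contact lens as a vehicle to transfer the VCO need to be further investigated". The Literature review says of VCO that "one of the discomforts when using the VCO, it is oily and messy when used directly on eyes", and that components of it "may act as protective layer over the tear film layers to reduce evaporation".

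Statistical Analysis specifies a repeated-measures ANOVA for the before, immediate and after readings at the 0.05 level. It names no lens factor, no time-by-lens interaction and no deciding time point.

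**The concern.** The wet length of a strip does not identify the liquid that wetted it. The VCO eye has just been given a second liquid, by design; nothing indicates that the placebo eye has. Phase 2 describes no rinse, blot or wait between lens removal and the strip, and no second method of measuring tear volume could contradict a misleading reading.

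The placebo lens controls for insertion, wear, removal and the strips themselves, but not for anything specific to the oil. Randomising which eye receives VCO does not help, because an oil-related artefact follows the lens. Averaging three strips or enrolling more subjects does not help either, because neither removes a systematic shift.

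At stake is half of the hypothesis. Since either post-wear reading could be used, an immediate rise in the VCO eye could be reported as improved tear volume although the plan cannot say what produced it.

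**Working it through.** There is no figure in the plan to reproduce: the 50 subjects are stated without an effect size, SD or power. The check is therefore a decomposition of the reading, followed by an illustration.

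**1. What each comparison contains.** For the change from pre-insertion to the immediate reading, write T for the change in tears apart from reflex responses, H for reflex tearing from handling and strips (both eyes), O for any effect of residual oil on strip wetting, and R for any extra VCO-specific reflex response.

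- VCO eye: T(VCO) + H + O + R
- Placebo eye: T(placebo) + H
- Between eyes: [T(VCO) − T(placebo)] + O + R

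H cancels between eyes; O and R do not. In a time-only comparison within the VCO eye, the kind that Statistical Analysis names, H does not cancel either.

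**2. What the documents say about O and R.** They give no VCO load, residual amount, strip behaviour with oil, or human irritation figure. O could be positive (the strip takes up oil) or negative (oil slows aqueous wicking). R could be positive (irritation) or negative (a soothed eye tears less). Neither sign is documented.

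**3. Illustration: paired between-eye test.** Assumptions: no true effect, n = 50 complete pairs, two-sided 5% (the plan does not state sidedness), artefact b in SDs of the between-eye difference. The noncentrality is b × √50 = 7.071b, with 49 degrees of freedom.

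| b (SD) | 7.071b | Chance of p<0.05 |
|---|---|---|
| 0 | 0 | 5.0% |
| 0.1 | 0.707 | 10.7% |
| 0.2 | 1.414 | 28.4% |
| 0.3 | 2.121 | 54.8% |
| 0.4 | 2.828 | 79.2% |
| 0.5 | 3.536 | 93.4% |

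For comparison, by the normal approximation, the effect detectable with 50 pairs is (1.960 + 0.842)/√50 = 0.396 SD at 80% power and (1.960 + 1.282)/√50 = 0.458 SD at 90%. An artefact of that size would look like a real effect. A negative artefact of the same size would give the same rejection rate in the other direction, or hide a true benefit.

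**4. Illustration: time-only ANOVA in the VCO eye.** Assumptions: a non-therapeutic shift b (in between-subject SDs) at the immediate reading only, compound symmetry with correlation ρ, and F on 2 and 98 degrees of freedom. The noncentrality is λ = 50 × (2/3)b² / (1 − ρ).

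| b | ρ | λ | Chance of p<0.05 |
|---|---|---|---|
| 0.2 | 0.5 | 50 × 0.0267/0.5 = 2.67 | 28.2% |
| 0.2 | 0.7 | 50 × 0.0267/0.3 = 4.44 | 44.4% |
| 0.3 | 0.5 | 50 × 0.06/0.5 = 6.00 | 57.0% |
| 0.3 | 0.7 | 50 × 0.06/0.3 = 10.00 | 80.3% |

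Here the shift may be handling-related tearing alone, with no oil effect. The placebo eye would show the same shift, but the plan names no comparison that would use it.

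Every b, SD and ρ is assumed. The tables show how a shift becomes a significant result; they do not estimate what will happen in this trial.

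**The case against.** The strongest reply is that neither mechanism is documented. The oiliness, messiness and blurring in the Literature review refer to VCO applied directly to the eye, not through a lens, and irritation and tearing are not mentioned. The ISO ocular irritation test listed under Phase 4 is one of several biocompatibility tests and is not evidence that the lens irritates. What the Literature review does report points the other way: no harmful effects in rabbit eyes, anti-inflammatory components, and a human study in which tear volume rose. A real rise is thus an expected effect. The placebo eye shares all handling-related reflex tearing, and a reading 15 minutes after removal is already scheduled, which helps to separate a brief artefact from a lasting change.

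All of this stands as a limit on what may be claimed. A reader might infer that the strip does absorb oil, that VCO irritates the eye, or that the bias necessarily favours VCO. The documents support none of these.

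The reply does not show that the immediate reading measures tear volume. Absence of harm in rabbits is not absence of extra tearing in people, and an expected true rise does not make an observed one attributable. The later reading helps only if the plan says that it decides.

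**Conclusion.** The concern holds as a limit on interpretation. The plan cannot exclude residual oil or an extra VCO-specific reflex response as the cause of a between-eye Schirmer difference at the immediate reading. Separately, a before/immediately/after comparison without a lens contrast could credit handling-related tearing to VCO.

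This rests on four features of the plan: one instrument for tear volume, a lens intended to transfer oil, no oil described in the placebo, and no stated deciding reading or between-eye test. It needs no assumption about the artefact's size. That size and its direction remain unknown, and the percentages above must not be quoted as this trial's false-positive risk. The point merits a wording change; it does not show the design to be invalid.

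**What to change.** In Objective, Statistical Analysis and Phase 2:

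- State that the tear-volume claim is decided by the Schirmer reading 15 minutes after lens removal, compared as VCO eye versus placebo eye within subject and adjusted for the pre-insertion reading. One way is to regress the between-eye difference at that time on the between-eye difference before insertion and test the intercept. This choice also fits the prolonged-relief aim in the Exec Summary.
- Keep the immediate reading as secondary, labelled *strip wetting (may include residual VCO)*.
- Optionally record an irritation score for each eye as descriptive context. Do not use it to veto a result. With no threshold, and ignoring ties, the VCO eye's mean would be the higher one about half the time by chance even if the lenses irritated equally, and such a rule would then block a genuine effect. The score would not detect oil uptake in any case.

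Cost: a few sentences, no new visit and no new Schirmer reading; the optional score takes a few seconds per eye. The sponsor gives up the ability to support the claim with an immediate rise alone. Some oil may still be present at 15 minutes, so the ambiguity is reduced, not removed, and the report should say so.

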## Research Question

## Literature review

Dry eye is an ocular condition which is characterized by reduction in tear volume, tear stability and increase in tear osmolarity as well as water evaporation. Visual disturbances including blurriness, visual discomfort and damage of the ocular surface are the most common dry eye-related sign and symptoms. Previous study had reported that 25 % of patients who visited ophthalmic clinic may report symptoms of dry eye. Thus, making this condition as one of the public health. The current study of dry eye prevalence of in Kuala Lumpur, Malaysia, showed the results of estimation that around 15% of the sample population suffering dry eye (Kaur et.al., 2016). However, the prevalence of dry eye varies between countries and was estimated to be around 7.4% to 33.7% (Buckley, 2018).

To ensure the accuracy of dry eye diagnosis, different tests of tear parameters including tear quantity and quality tests are used to detect the pre-existing condition (Masmali et al. 2016). One of the ways to assess for tear quality is by assessing the stability of the tear film which can be obtained through tear break up time (TBUT) measurement. Tear quantity can be obtained by measuring the tear volume and Schirmer's test is one of the objective measurements that is widely used by the practitioner to measure it (Miyake et. al, 2016). It becomes practically important as stability of the tear film and sufficient composition of each substances such as lipid, mucin, electrolytes, and including aqueous humor, are crucial in order to know the integrity of the tear film layer (Buckley, 2018).

At present, there are few dry eye remedies available in the market. Among all of those remedies, artificial tear and eye lubricants are still the most common initial management and prophylaxis that will be given by medical practitioners to dry eye patient regardless of the type of dry eye. Artificial tear is well known to given temporary relief of dry eye's sign and symptoms. Though, it might not be an effective treatment as they only contain polymers that is able to lubricate ocular surface and lack of numerous important biological factors such as antimicrobial growth and anti-inflammatory factors that present in natural tear and important to maintain ocular surface homeostasis (Mutalib et al. 2015)

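### Phase 2 averages three Schirmer strips per time point with no spacing stated, so earlier strips may shift the tear-volume value and its change over time

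*Combined protocol and SAP*

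**What the plan says.** The Literature review presents Schirmer's test as a measure of tear quantity: "Tear quantity can be obtained by measuring the tear volume and Schirmer's test is one of the objective measurements". Phase 2 is the only phase that uses it; Phases 1, 3 and 4 measure TBUT. Phase 2 therefore supplies all the tear-volume data for objectives (i) and (ii), including "To determine the tear break up time (TBUT) and tear volume (Schirmer's Test) at 15 minutes after lens removal".

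The Phase 2 sequence is:

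- Baseline Schirmer's test "on both eyes will be taken before lens insertion".
- A VCO lens in one eye and a placebo hydrogel lens in the other: "Subjects will wear the contact lenses for 15 minutes".
- Then "both contact lenses will be removed and second measurements of Schimer's Test will be done".
- The averaging rule: "All measurements will be taken three times and the average value will be used as the data".
- The label for the averaged post-wear value: "These will be the immediate measurement after therapeutic VCO contact lens wear".
- Finally, "Subjects will be given 15 minutes time interval before a re-measurement of Schimer's Test again".

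Phases 3 and 4 use the same averaging sentence for TBUT, and Phase 1 uses a close variant. Phase 2 does not state how long a strip stays in place, how far apart the three strips are, or whether the three readings are kept separately. The Statistical Analysis section plans a repeated-measures ANOVA across before, immediate and after. It names no factor for eye (VCO or placebo) and does not mention repeat readings.

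**The concern.** Averaging reduces noise when the readings are replicates of the same quantity. A Schirmer strip absorbs the fluid it measures and touches the eye, so a second strip used soon after the first meets an eye that the first has altered. Depletion would lower the later readings and reflex tearing would raise them. Averaging cannot remove a systematic shift of either kind.

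Two things are at stake. First, the value labelled as immediate may not reflect tear volume at lens removal. Second, the lens goes onto an eye that has just been sampled three times. Any lasting effect of those strips then enters the wear period and the later readings, where it cannot be told apart from change over time within an eye.

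**Working it through.** The plan gives no figure to reproduce here: there is no strip duration, Schirmer SD or expected effect. The check is a count followed by an illustration. The per-strip change r and the minutes per strip are assumptions.

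**Strip count (Phase 2, natural reading of the rule).** 3 readings × 3 time points = 9 strips per eye, and 9 × 2 = 18 per subject. One reading per time point gives 3 per eye and 6 per subject.

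**Shift within a time point.** If each strip changes the next reading by a fraction r, the average divided by the undisturbed value is k = [1 + (1+r) + (1+r)²] / 3.

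- r = -10%: (1 + 0.90 + 0.81)/3 = 0.90
- r = -20%: (1 + 0.80 + 0.64)/3 = 0.81
- r = +10%: (1 + 1.10 + 1.21)/3 = 1.10
- r = +20%: (1 + 1.20 + 1.44)/3 = 1.21

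If the eye recovers fully between time points and r is constant, k is the same at all three. Absolute values and absolute changes are then scaled by k, and percentage change is unaffected.

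**Carry-over between time points (worst case, no recovery).** Three strips separate corresponding readings at successive time points, so the apparent change from baseline with no lens effect is (1+r)³ - 1 after removal and (1+r)⁶ - 1 at the last time point.

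- r = -5%: 0.95³ - 1 = -14%; 0.95⁶ - 1 = -27%
- r = +5%: 1.05³ - 1 = +16%; 1.05⁶ - 1 = +34%

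With one strip per time point the exponents become 1 and 2:

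- r = -5%: -5%; 0.95² - 1 = -10%
- r = +5%: +5%; 1.05² - 1 = +10%

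**Timing.** At an assumed 1 to 5 minutes per strip, with both eyes tested together, three strips take 3 to 15 minutes. At the upper end, the immediate value takes as long as the 15-minute interval before the next measurement. Wear plus interval is 15 + 15 = 30 minutes. Nine strips add 9 to 45 minutes, for a visit of 39 to 75 minutes. The text after Phase 4 puts the procedure at under half an hour, which leaves no evident allowance for recovery between strips.

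**The case against.** Several counter-arguments have force.

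- **Spacing and count are inferred.** The protocol does not say that the strips follow one another directly. The averaging sentence sits beside the post-removal reading, so it could be read as covering that time point alone. The natural reading covers all three, and the label of immediate leaves little room for spacing, but both remain inferences. Phase 2 also cites a study of a modified Schirmer test, which may define strip time and uptake. That source was not available to this review.
- **The placebo eye has the same strips.** An additive shift common to both eyes cancels in a VCO-minus-placebo comparison. This stands, with two limits: a proportional shift, or one that differs between an oil-treated and an untreated eye, would not cancel exactly, and the analysis section does not name that comparison.
- **Scaling alone does not cost power.** A reader might infer that averaging dilutes the VCO effect and so weakens the test. The documents do not support that. A constant k shrinks the between-subject spread along with the difference. If strip noise is independent and additive (an assumption), averaging three divides it by √3, to 0.577. Signal-to-noise on that component, relative to one strip, is then 0.903/0.577 = 1.56 at a 10% loss per strip and 0.813/0.577 = 1.41 at 20%. At 50%, k = (1 + 0.5 + 0.25)/3 = 0.583, giving 0.583/0.577 = 1.01. On that model the average does no worse than a single strip up to about a 50% loss.
- **TBUT.** The documents do not say whether TBUT is measured with a dye, so no general contrast between the two tests is drawn here.

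**Conclusion.** The concern holds as a risk of bias in measurement. The averaging rule is applied to a test whose repeats may not be replicates, in the only phase that measures tear volume. The exposed quantities are the absolute tear volume and the within-eye before/immediate/after change, which is the one comparison the Statistical Analysis section names and the one in which a testing effect is confounded with time.

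The illustrated size is an average of 0.81 to 1.21 times the undisturbed value for assumed changes of -20% to +20% per strip. This rests on three premises: the strips are taken close together, the rule covers all three time points, and one strip affects the next. The first two are readings of the text. The third follows from how the test works, and the documents do not quantify it.

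A reader might go further and conclude that the tear-volume result is invalid. The documents do not support that: the size and sign of any carry-over are unknown, and the fellow eye offers partial protection if the eyes are compared. This is an inexpensive improvement worth making, not a demonstrated failure of the endpoint.

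**What to change.** Amend Phase 2 to take and analyse one Schirmer reading per eye before insertion, one immediately after removal and one at the 15-minute point. State the strip duration. Leave the TBUT averaging rule in Phases 1, 3 and 4 unchanged.

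If three strips are kept, state their spacing, record them in order, analyse the first as the main value and report the average as a sensitivity analysis. This alternative removes the shift within a time point but not the carry-over from baseline strips.

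Under either option some carry-over between time points remains. The Statistical Analysis section should therefore rest the Phase 2 result on the VCO-minus-placebo difference in change from baseline.

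The change needs only wording in Phase 2 and the Statistical Analysis section. It cuts strips from 18 to 6 per subject and shortens the visit. The real cost is precision: a single reading is noisier than an average, and if strip noise is large and carry-over small, that loss could outweigh the bias removed. The documents give no data to settle this.

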## Exec Summary

Dry eyes is an extremely common symptom that affects as many as 337 million people globally. Almost everyone has probably had or will have dry eyes at some point in their life. Common treatment to dry eyes is by using lens lubricant or eye drops which gives short relief and comfort. Sufferers would have to endure the discomfort of having to instill drops frequently for which will indirectly affect their work and quality of life. This study will determine the role of VCO therapeutic contact Lens in changing the tear volume and improving tear stability on dry eyes patients by giving a long relief and effective remedy.

The study will be conducted at UKM Optometry Clinic using randomized, double-masked on 50 dry eye subjects in 4 different phases. Measurement of tears before and after (15 minutes) the therapeutic VCO contact lens are worn by the subjects will be recorded. Similar parameter will be measured 15 minutes post wear (Phase 1 & 2). The intra-variability and inter-variability of the parameters will also be measured accordingly after 2 months (Phase 3 & 4).

The outcome of this study is expected to enhance the volume and stability of tears in dry eye subjects. Sufferers of these symptoms will find prolonged relief through this new knowledge of management, thus will improve the quality of life of people who has dry eyes problems.

VCO therapeutic contact lens may provide the solution of prolonged relief for dry eye symptoms. This will provide a new knowledge amongst eyecare practitioners in managing patients with dry eyes due to ocular disease or environmental factors and using a local product will indirectly boost the economic growth of Malaysia.

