## STATISTICAL ANALYSIS

After the data has been collected, IBM SPSS Statistics Version 25 (Armonk, NY, USA) will be use to analyze the data. The assessment of the efficacy will be based on the all subjects who completed the study. Shapiro-Wilk test will be used to test the normality of the data as the sample size is less than 100. All results are expressed as Mean  $\pm$  SD. **Parametric test of Repeated Measured Anova** will be used to analyze the statistical difference of before, immediately and after treatment if the data is normally distributed. A probability value ( $p$ -value)  $<0.05$  will indicate that the data is statistically significance.

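### Does Phase 2 put the last Schirmer reading at a later time than the one objective (ii) names?

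*Combined protocol and SAP*

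**What the plan says.** Objective (ii) fixes the last TBUT and Schirmer readings "at 15 minutes after lens removal". The Exec Summary agrees: "Similar parameter will be measured 15 minutes post wear (Phase 1 & 2".

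The Phase 2 section describes the Schirmer session. A baseline reading is taken and the lenses are worn for 15 minutes. Both lenses are then removed and the second readings follow. On replication it says "All measurements will be taken three times and the average value will be used as the data", and it labels the second readings: "These will be the immediate measurement after therapeutic VCO contact lens wear". Next comes "Subjects will be given 15 minutes time interval before a re-measurement of Schimer's Test again". It gives no starting point for the interval, no duration for a Schirmer test, and no statement on whether the eyes are tested together or in turn.

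Phase 1 has parallel wording for TBUT ("Subjects will be given 15 minutes time interval before a re-measurement of TBUT test again"), and Phases 3 and 4 follow the same pattern. Under Statistical Analysis, the repeated-measures ANOVA "will be used to analyze the statistical difference of before, immediately and after treatment". On lens allocation, Phase 2 says "The contact lenses will be fitted in randomized manner by a mask operator".

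**The concern.** Three Schirmer tests take time, and the interval is mentioned only after them. A technician who works down the page would finish the triplicate set, wait 15 minutes, and only then start the last set. That reading falls later than the time named in objective (ii), by the length of the triplicate set.

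This would matter for three reasons. Schirmer is the only tear-volume outcome and Phase 2 is its only session, since Phases 3 and 4 repeat TBUT alone. The after level of the ANOVA is the one whose timing is unclear. Two operators could also time it differently without either recording a deviation, which would add timing scatter between subjects. For TBUT, a different habit in different phases would add to the variability that objective (iii) sets out to measure.

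**Working it through.** **Inputs.** From Phase 2: 15 minutes of wear, three replicates per reading, a 15-minute interval. From objective (ii): a target of 15 minutes after removal. From the Exec Summary: 50 subjects. Assumed, because the documents do not say: t minutes per Schirmer test, taken from 0.5 to 5, with eyes tested either together or in turn (three tests in one eye, then three in the other).

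**The plan's own figure.** With removal at time 0 and the interval counted from removal, the last set starts at 15 minutes, as objective (ii) says. With the interval counted from the end of the immediate set, it starts at 15 + 3t (together) or 15 + 6t (in turn). That equals 15 only if t = 0.

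| t (min) | Last set starts, written order, together: 15 + 3t | Same, in turn: 15 + 6t | Rest left if counted from removal, together: 15 − 3t | Same, in turn: 15 − 6t |
|---|---|---|---|---|
| 0.5 | 16.5 | 18 | 13.5 | 12 |
| 1 | 18 | 21 | 12 | 9 |
| 2 | 21 | 27 | 9 | 3 |
| 3 | 24 | 33 | 6 | −3 |
| 5 | 30 | 45 | 0 | −15 |

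The delay is real for any positive t. Its size, from 1.5 to 15 minutes with eyes together, comes entirely from the assumed t.

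**VCO against placebo.** With eyes together, the two eyes are read at the same moments, so the delay is common to both. With eyes in turn, the second eye runs 3t behind the first at the immediate and the last reading alike. The spacing between those two readings is still equal in the two eyes: 15 + 6t in the written order, 15 if counted from removal. The lag would load onto one lens only if test order followed lens type, and nothing in the documents says it does. Suppose the right eye always goes first and lenses are randomised to eyes subject by subject (an assumption). Each subject's lag is then +3t or −3t with mean 0, and the mean over 50 subjects has SD 3t/√50. At t = 1 this is 3/7.07 = 0.42 minutes; at t = 2.5 it is 7.5/7.07 = 1.06 minutes.

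**The ANOVA.** The analysis compares three labelled occasions. Clock minutes are not a term in the plan, so the analysis can be run under either reading.

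**Session length.** Wear plus interval is 15 + 15 = 30 minutes before any measuring time. The remark at the end of the Phase 4 section that the procedure lasts under half an hour is therefore loose under both readings. No estimate depends on it.

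**The case for a change.** The strongest case for a change is that Phase 2 is the only operating instruction for the Schirmer test. Intent stated in the objectives does not reach the person holding the strip, and timing that was never recorded cannot be recovered. The discrepancy is certain in the written order, and wording to remove it would cost a few sentences.

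The textual part of this stands: Phase 2 does not name its anchor. The rest is weaker. Silence in the procedure, set beside two explicit statements elsewhere that agree with each other, is a gap staff can fill by reading the protocol as a whole. The wording is parallel across Phases 1 to 4, so one site with one habit would time all phases alike. That limits the worry about objective (iii).

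A tighter rule is also not free. Counting from removal shortens the rest between sets to 15 − 3t minutes with eyes together, which is zero at t = 5. With eyes in turn the immediate set is still unfinished at 15 minutes for any t above 2.5. A narrow window, say under 3 minutes after the 15-minute mark, would reject the second eye's last set in every subject tested in turn, since that set starts at 15 + 3t = 18 to 22.5 minutes for t = 1 to 2.5. Whether a stricter clock is worth this depends on the test duration, which the documents do not give.

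**Conclusion.** No change to the plan follows. Phase 2 omits a detail that objective (ii) and the Exec Summary supply: the last reading is due 15 minutes after lens removal. Read literally and alone, Phase 2 puts it 3t minutes later with eyes together, which is 1.5 to 15 minutes for an assumed t of 0.5 to 5.

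What is exposed is the exact clock time attached to one of three occasions, and its consistency between subjects. The within-subject lens comparison is not shown to be biased. That conclusion assumes both eyes follow the same sequence and that test order is not tied to lens type. The effect on Schirmer values is unknown, because the documents give neither a test duration nor a rate of tear change. If the literal order was followed, an analyst can describe the last occasion as about 15 minutes after the immediate set and run the same analysis. The half-hour remark is a clerical slip with no bearing on any result.
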